5.5.2 Laboratory evaluations

A baseline laboratory evaluation is defined as the last evaluations prior to the first dose (screening period).

The worst grade (abnormality grade sorted from high to low: abnormality with clinical significance > abnormality without clinical significance > normal) of results of such laboratory evaluations as hematology, clinical chemistry, myocardial zymography, coagulation function, routine stool, urinalysis, thyroid function tests (T3, T4, FT3, FT4, and TSH) at baseline and post-baseline of each dose group will be summarized using a shift table.

All laboratory evaluations will be listed by subject ID and indicated for clinical significance if any.

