16. Pulmonary function test: Maximum vital capacity, the forced expiratory flow at 25-75% of forced vital capacity (FEF25-75), the peak expiratory flow rate (PEF), the maximum expiratory volume per second, diffusing capacity of the lungs for carbon monoxide (DLCO) and oxygen saturation, which will be performed during the screening period and based on clinical indicators as determined by the investigator thereafter. Arterial blood gas test: optional. This test includes partial arterial pressure of oxygen (PaO₂), partial arterial pressure of carbon dioxide (PaCO₂), arterial oxygen saturation (SaO₂), and pH, and can be performed during the screening period. Pulmonary function test and arterial blood gas test indicators will be based on the actual conditions at each site.
17. Immunogenicity blood samples will be collected once within 0.5 h before SHR-1210 infusion on D1 of cycle 1, cycle 2, and the third cycle of every three cycles thereafter (cycles 5, 8, 11, etc.), once at the end of the treatment, and once per month at safety follow-ups after withdrawal for 3 times (if applicable). In case of national holidays, the blood collection time may be adjusted as appropriate. If the subject develops SHR-1210 infusion-related reactions, blood samples should be collected as close as possible to the onset of the event, to the end of the event, and about 30 days after the end of the event, for immunogenicity comparison and analysis. Immunogenicity blood samples should be collected following the study protocol. However, if deemed necessary by the investigator, unscheduled immunogenicity blood samples may be collected. Tests will be performed at the central laboratory. Four (4) mL of blood will be collected each time for immunogenicity.
18. The safety assessment for AEs and laboratory tests will be performed according to NCI CTCAE v4.03. All AEs/SAEs will be recorded in the CRF from the time of signing the ICF to the end of safety follow-up or the start of new anti-tumor therapy (whichever occurs first). The definition, recording, causality assessment, severity assessment, reporting time limit, handling, and follow-up of AE and SAE should refer to the description in Section 9 of the protocol.

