3.2 Study Endpoints

3.2.1 Primary endpoints

- Incidence of AEs evaluated per CTCAE 4.03, especially the incidence of AEs meeting any of the following criteria:
 - Hematologic toxicity
 - Grade 4, or
 - Grade ≥ 3 thrombocytopenia with hemorrhage, or
 - Grade ≥ 4 neutropenia with pyrexia and infection
 - Grade ≥ 3 non-hematologic toxicity (except for laboratory abnormalities), hypertension, rash, diarrhea, nausea and vomiting that cannot be controlled after symptomatic treatment
 - Grade ≥ 3 laboratory abnormalities that lead to medical interventions or hospitalization, or last for ≥ 7 days
 - Any Grade 5 AEs
- ORR evaluated as per RECIST v1.1

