9.1.1 Definition of AE

AE refers to any untoward medical condition in a clinical study subject who receives a pharmaceutical product, and the condition does not necessarily have a causality with the treatment. All AEs from signing of the informed consent form to the end of the safety follow-up period (90 days after the last dose) or the start of other anti-tumor treatments will be collected in this study. AEs can include any unfavorable and unintended symptoms, signs, abnormal laboratory findings, or diseases, including the following:

- 1) Worsening of pre-existing (prior to entering the clinical trial) medical conditions/diseases (including worsening symptoms, signs, or laboratory abnormalities);
- 2) Any new AE: Any new adverse medical conditions (including symptoms, signs, and newly diagnosed diseases);
- 3) Clinically significant abnormal laboratory findings.

All AEs should be documented in detail by the study personnel, including: the name of the AE and description of all relevant symptoms, onset time, severity, causality assessment, duration, measures taken, as well as final results and outcomes.

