5.5 Safety Analysis

Unless otherwise specified, the safety statistical analysis will be summarized and tabulated by the treatment group. All safety analyses will be conducted based on the SS. Normal and abnormal parameters for safety evaluation will be summarized based on scheduled and unscheduled visits. Single unscheduled examinations will only be listed.

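### No SAP section derives a CTCAE grade from the laboratory values, so a persistent Grade ≥ 3 result that is not recorded as an adverse event can go uncounted

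*SAP*

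**What the plan says.** Protocol Table 1, note 18: "The safety assessment for AEs and laboratory tests will be performed according to NCI CTCAE v4.03". Protocol 3.2.1 makes Grade ≥ 3 "laboratory abnormalities that lead to medical interventions or hospitalization, or last for" 7 days or more one component of the primary safety endpoint.

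SAP 5.5.2 describes a shift table from baseline to the worst post-baseline result. Its ordering is given as "abnormality grade sorted from high to low: abnormality with clinical significance", followed by abnormal but not clinically significant, then normal. The accompanying listing carries the same flag: "All laboratory evaluations will be listed by subject ID and indicated for clinical significance if any". Neither output uses a CTCAE grade.

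SAP 5.5.1 works from AEs. It grades every AE by CTCAE v4.03, counts the highest grade per subject, summarizes Grade ≥ 3 treatment-emergent AEs, and analyses the Grade ≥ 3 laboratory component separately. It also summarizes laboratory abnormalities seen in at least 10% of subjects.

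On unscheduled tests, SAP 5.5 has two sentences close together. One reads "Normal and abnormal parameters for safety evaluation will be summarized based on scheduled and unscheduled visits"; the next reads "Single unscheduled examinations will only be listed".

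**The concern.** The protocol names an objective scale for laboratory tests, and the SAP's laboratory section uses a judgement-based one. SAP 5.5.2 calls its top category the worst grade, but a reader cannot recover a CTCAE grade from it.

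This matters most for the part of the primary component defined by duration. Intervention and hospitalization leave their own trace in the data. A Grade ≥ 3 value that simply persists for 7 days needs neither, so it enters the analysis only if the site records an AE. Acceptable safety is one of the two conditions in Protocol section 4 for considering further development, so the laboratory part of that judgement should not rest solely on how consistently about 20 centers turn laboratory results into AE entries.

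If single unscheduled tests are left out of the worst-value table, the table may also omit the very results that were obtained because toxicity was suspected.

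**Working it through.** The plan states no rate of laboratory toxicity, so there is no figure to reproduce. The check is a comparison of the texts, followed by two illustrations on stated assumptions.

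**1. Where could a Grade ≥ 3 laboratory value be counted?**
- SAP 5.5.2 shift table: three levels, no CTCAE grade.
- SAP 5.5.2 listing: all results, clinical-significance flag, no CTCAE grade mentioned.
- SAP 5.5.1, Grade ≥ 3 treatment-emergent AEs and the primary laboratory component: CTCAE grade present, source is the AE record.
- SAP 5.5.1, abnormalities at 10% or more: no grade mentioned, and the text does not say whether the source is values or AEs. With 45 subjects (Protocol 10.1; 6 from Stage I plus 39 from Stage II), 4/45 = 8.9% falls below the cut-off and 5/45 = 11.1% reaches it, so any abnormality seen in 4 subjects or fewer is not shown.

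Every graded count therefore passes through an AE record.

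**2. Does every such value become an AE?** Protocol 9.1.1 names "Clinically significant abnormal laboratory findings" among the inclusions, but its lead-in also admits abnormal laboratory findings generally. Protocol 9.1.3 asks that abnormal laboratory changes on treatment be documented. These texts do not restrict AEs to clinically significant values; nor do they state that every Grade ≥ 3 value must be entered as one. That leaves room for sites to differ.

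**3. Are unscheduled results in the worst-value table?** The two SAP 5.5 sentences point in different directions, and SAP 5.1.5 adds that post-baseline data are summarized by protocol visit. A programmer could defend either reading.

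**4. What could be lost if unscheduled results are left out of the table?** Hematology and chemistry are scheduled before each SHR-1210 dose, nominally every 14 days (Table 1, note 8). Assume random onset and exact spacing. The chance that an abnormality lasting *d* days falls on a scheduled test is min(1, *d*/14):
- 3 days: 3/14 = 21%
- 7 days: 7/14 = 50%
- 10 days: 10/14 = 71%
- 14 days or more: 100%

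An abnormality of 7 to 13 days meets at most one scheduled test at this spacing, so scheduled results alone cannot show that it lasted 7 days.

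**5. What could be lost through AE recording?** Assume 45 subjects and a true Grade ≥ 3 laboratory rate of 20%, giving 45 × 0.20 = 9 subjects. Number counted = 9 × share recorded as AEs:
- 100%: 9.0 (none lost)
- 90%: 8.1
- 75%: 6.75, about 6.8
- 50%: 4.5

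Neither the 20% nor the recording shares come from the documents. The range includes no loss at all.

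**The case against.** The strongest reply is that SAP 5.5.2 is not where Grade ≥ 3 toxicity is counted. SAP 5.5.1 does that, on the CTCAE scale, with a dedicated analysis of the primary laboratory component and no restriction to scheduled visits. This stands. A reader might infer from 5.5.2 that such toxicity is under-counted, or that the shift table is the SAP's only laboratory analysis. The documents support neither reading.

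A reader might also infer that a value becomes an AE only when judged clinically significant. Protocol 9.1.1 and 9.1.3 are wider than that.

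The route to a missed event is narrow. The value must be Grade ≥ 3, persist, prompt no intervention and produce no AE record. Protocol Tables 7 and 8 link many hematologic, hepatic and renal reactions of that severity to treatment interruption or discontinuation, which makes an AE record likely. This too stands, and it is a reason to expect a small effect.

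Two further limits apply. The Stage I review in SAP section 6 uses listings of AEs and laboratory evaluations, so the form of the shift table does not bear on the choice of Stage II group. And SAP 5.5.2 does not say who judges clinical significance; Protocol 8.2.3 assigns this to the investigator for ECGs, and extending it to laboratory tests is an inference. Since every group receives both drugs and there is no control group, an argument from open-label bias adds little.

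What the reply does not remove is the mismatch itself: the protocol's scale for laboratory tests appears nowhere in the analysis of laboratory values, and nothing checks the AE-based count against them.

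**Conclusion.** The gap is real in the text but limited in reach. No SAP section derives a CTCAE grade from laboratory values, although Protocol Table 1, note 18, calls for assessment on that scale. The primary laboratory component is analysed, but only through AE records, and its duration limb is the exposed part. SAP 5.5 is unclear, rather than plainly exclusionary, about unscheduled results.

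The size is unknown and may be zero. The coverage figures of 21% to 71% assume random onset and exact 14-day spacing, and describe scheduled tests only. An event missed by the shift table still enters the SAP 5.5.1 counts if it is recorded as an AE. The counts of 4.5 to 9.0 out of 9 subjects rest on an assumed rate and assumed recording shares. No number of missing subjects should be quoted as a finding.

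The change is still worth making. It puts the protocol's own objective scale into the laboratory analysis, uses data already collected, and gives an independent check on a primary safety component.

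**What to change.** In SAP 5.5.2, add a shift table from baseline to worst post-baseline CTCAE v4.03 grade, derived by program from all scheduled and unscheduled values for tests with numeric criteria. Keep the clinical-significance table as supportive.

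In SAP 5.5.1, cross-check the component for Grade ≥ 3 abnormalities lasting 7 days or more against laboratory result dates together with AE start and end dates. Both sources are needed, because two-weekly tests alone often cannot establish 7 days. Any Grade ≥ 3 result with no matching AE should be listed and queried before database lock.

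In SAP 5.5, reconcile the two sentences so that unscheduled results count in worst-value tables. By-visit summaries can stay restricted to scheduled visits.

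The cost is SAP wording, programming and mapping of each center's local reference ranges. No further tests on subjects are needed, since all laboratory evaluations are already collected and listed. The downside is that reported laboratory toxicity rates may look less favourable.

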5.5.3 Vital signs

Vital sign measurements at each scheduled visit point (including baseline) will be summarized and listed using descriptive statistics. Changes in vital signs from baseline at each visit point after baseline will be summarized and listed using descriptive statistics.

Baseline is defined as the last measurement before the first dose.

5.5.4 Electrocardiogram

Normal/abnormal ECG changes from baseline at each visit point after baseline will be summarized using a shift table. ECG results will be listed.

5.5.5 Physical examination

Physical examinations are only listed for reporting.

5.5.6 ECOG PS

The ECOG PS of each dose group will be analyzed using descriptive statistics. The worst ECOG PS at baseline and post-baseline will be summarized using a shift table.

All ECOG PS will be listed.

5.5.7 Other safety analyses

Pituitary-adrenal axis test, echocardiography, pulmonary function examination, arterial blood gas analysis, virology, blood pregnancy test, and tumor tissue sample collection are listed in detail.

6 INTERIM ANALYSIS

It is planned that after the 18th subject in Stage I completes Cycle 1 treatment (28 days), a safety analysis will be conducted. The leading center's principal investigator and the sponsor will jointly perform a safety assessment of subjects enrolled in Stage I and decide the treatment groups of Stage II.

This analysis only provides a listing of subjects' AEs and laboratory evaluations and does not involve the analysis of the efficacy endpoints.

7 REFERENCES

8 APPENDICES

8.1 Appendix 1. Best Overall Response with CR and PR to Be Confirmed

Overall Response at First Time Point	Overall Response at Subsequent Time Point	Best Overall Response
CR	CR	CR
CR	PR	SD, PD or PR ^a
CR	SD	SD (provided minimum criteria for SD duration met, otherwise, PD)
CR	PD	SD (provided minimum criteria for SD duration met, otherwise, PD)
CR	NE	SD (provided minimum criteria for SD duration met, otherwise, NE)
PR	CR	PR
PR	PR	PR
PR	SD	SD
PR	PD	SD (provided minimum criteria for SD duration met, otherwise, PD)
PR	NE	SD (provided minimum criteria for SD duration met, otherwise, NE)
NE	NE	NE

Note: CR is complete response, PR is partial response, SD is stable disease, PD is progressive disease, and NE is non-evaluable. a: If a CR is truly met at first time point, then any disease seen at a subsequent time point, even the disease meeting PR criteria relative to baseline, makes the disease PD at that point (since disease must have reappeared after CR). Best overall response will depend on whether minimum duration for SD is met. However, sometimes CR may be claimed when subsequent scans suggest small lesions are likely still present and in fact the subject has PR, not CR at the first time point. Under these circumstances, the original CR should be changed to PR and the best response is PR.
